**Phase 3 involves the repeat to the DDAVP stress challenge and a repeat salivary cortisol collection.**

Table 2 schematizes the structure of the whole protocol.

see uploaded Table 2

---

Week 1, phase 1: In-hospital phase, cocaine-dependent patients.

The purpose of the in-hospital phase is to allow abstinence to begin, and provide an environment amenable to stress sensitivity testing. Patients from either sites can be admitted to the General Research Unit on PI-5 for this phase, during which the following procedures will take place:

1) Establish controlled abstinence.

2) Complete baseline assessments, including Time Line Follow-Back (Litten & Allan, 1992) to quantify drug use, Cocaine Craving Scale (Weiss et al., 1997), Clinician Global Impression-Observer (Guy, 1976), Perceived Stress Scale (Cohen et al., 1983), Hamilton Depression Scale-25 items (Williams, 1988).

3) Upon the 1st negative urine toxicology for cocaine, we will collect baseline salivary cortisol samples at these approximate times: 8-9am, 11-12pm, 2-3pm, 5-6pm.

4) Stress Challenges. These consist of two tests performed on separate days in counterbalanced order, as illustrated below. The test itself will be performed in the Biological Studies Unit. Patients will have breakfast in the morning prior to testing.

**see uploaded Figure 1**

Each testing period will begin with the insertion of a saline lock. Following the saline lock insertion, there will be a 2-hour habituation interval before any testing begins. The testing will begin around noon to 1 pm, when the diurnal secretion of ACTH usually falls to allow easier detection of ACTH variation due to the experimental variations.

After habituation, baseline levels of ACTH, **BP, HR, subjective ratings of anxiety, restlessness, cravings for cocaine (Likert scales) are obtained. Research staff complete a behavioral activation scale during the endocrine challenge at those same specific time points ([name], personal communications). The patient is then asked to insufflate 40 IU (10 ug or 0.1cc) of desmopressin in each nostril.** At each of the specified time points in figure 1, repeat measurements of ACTH, BP, HR, subjective ratings, and **staff observer ratings are also obtained.** A relaxation procedure (specific muscle group tension and relaxation) used in protocol NYSPI IRB 6013, will also be used to close the day of testing. **At the next day of testing, the procedure begins by placement of a saline lock and habituation for two hours. Baseline levels of ACTH, BP, HR, subjective ratings and staff observer ratings are drawn. Then the patient is asked to insufflate 12 IU (16 ug or 0.3cc) of oxytocin in each nostril. Repeat measurements are obtained as during baseline occur at specified time points. Forty minutes later, patients insufflate 40 IU of desmopressin in each nostril, and all**

---

**measurements are repeated at specified time points.**

5) After baseline stress testing is completed, begin randomized administration of intranasal Oxytocin 20 IU per day in the morning, for each remaining day of phase 1. This will serve also as an opportunity to train patients on how to administer intranasal solutions. The steps are as follows: 1) exhale through the nose, head bent forward; 2) while inhaling, spray once into one nostril; 3) repeat step 1 & 2 for the other nostril; 4) repeat steps 1 to 3 again to reach the daily dose of 24 IU of randomized medication. The patients will be instructed by a member of the research staff to ensure proper technique and optimal absorption of the medication. The Oxytocin solution is stable at room temperature for one month after being opened. Nonetheless, the manufacturer recommends that the bottle be kept refrigerated between uses and we will recommend this to the patients as well. Its stability should ensure that transportation to the clinic should not cause degradation, provided it is not exposed to extreme heat (> 100 Fahrenheit), direct sunlight, or frozen.

Phase 1, control participants.

The purpose of Phase 1 for control participants without psychiatric, medical, or addiction disorders is to test their stress sensitivity with the same procedure as cocaine-dependent patients. This is to study if stress dysregulation is more prevalent among cocaine users than normal controls, and to study if vasopressin-based stress mechanisms bear some specificity to the stress dysregulation observed in cocaine-dependent patients.

For control participants, the procedure will be carried out over two days as outpatients. They will be instructed to present themselves between 9 to 10 am on a testing morning, having eaten breakfast. A saline lock will be inserted, and a 2-hour habituation period will follow before testing begins at approximately 1 pm. The procedure will be the same as described for cocaine-dependent patients, and will be administered in counterbalanced order (**see above, stress procedures**). Completion of phase 1 ends their participation in this study.

Phase 1, week 1, cocaine-dependent patients, outpatient version.

This procedure is based on our previous experience acquired during protocol NYSPI IRB 6013 (mifepristone study for cocaine dependence) with patients who cannot participate in the inpatient procedure. Over a period of 7 days, not counting Saturdays and Sundays, a participant will have to produce at least three consecutive cocaine negative urine toxicologies at daily visits. Once abstinence is established the phase 1 procedures begin (Table 1), with verification of negative toxicology before each testing day. Randomized medication will begin after completion of all the physiological tests.

---

If a urine toxicology test emerges positive for cocaine once Phase-1 procedures have begun, the testing will stop. The patient can then attempt another period of seven days to reach abstinence, complete the baseline testing, and begin randomized medication. If abstinence cannot be reached during this two-week window, the patient will be offered to carry out phase 1 as an inpatient. If the patient cannot participate as an inpatient, referrals to other treatment options will be offered.

Phase 2, outpatient phase, week 2 to 7, cocaine-dependent patients only

During this phase in which only cocaine-dependent patients participate, they will continue randomized medication while participating in a structured program to support and promote continuing abstinence and completion of the study.

For patients continuing at the STARS clinic and DOSA at Waters Place ([name]), the structure of the program during this phase will be as follows:

- 1: Patients continue to receive intranasal Oxytocin (24IU/day) vs. intranasal placebo. During their visits to either clinic, they will administer the randomized medication under supervision from a bottle kept at the clinic. Each witnessed administration will be recorded. Since they "self-administer" the medication, it can be witnessed by any member of the research team.
- 2: On the days when patients do not attend the clinic, they will be asked to administer the randomized medication from an "at-home" bottle. They will be asked to bring the bottle at each visit to the clinic. In a single-blind fashion, it will be weighed as a measure of compliance. The metered bottle delivers 4 IU/0.1cc or per puff. Each daily dosing requires 6 puffs, or 0.6cc. The weight of each puff or 0.1 cc is approximately 0.1g. Hence, for each at-home insufflation, the bottle weight is expected to change by 600 mg. The expected change in weight will be plotted against the recorded change in weight, and this will be used to estimate at-home compliance.
- 3: At each visit, vital signs are recorded, and an inquiry is made about adverse events. The Time-Line-Follow-Back is completed to review drug use by calendar date. This allows a day-to-day review of reported drug use for each day of participation.
- 4: At week 2, 4, and 6, a thorough medical review will be carried out to ensure patient safety. This will include a review of systems, with a focus on lethargy, fatigue, nausea, and weakness, which are the usual symptoms of hyponatremia. Although the risk is remote, hyponatremia would be the major metabolic complication that could arise from intranasal oxytocin. Of note is the fact that it has been reported when oxytocin is used in the induction of labor with continuous intravenous infusion (Pitocin, PDR, 2014), a condition vastly different from those of this study. A blood draw will be done to monitor electrolytes and

---

blood counts. For women, a urine pregnancy test will also be done. Detection of pregnancy ends participation in the study.

5: Self-reports that will be completed weekly at one of the visits: Perceived Stress Scale, Cocaine Craving Scale.

6: The vital sign form, the review of system form (including blood results) will be dated and will refer to a calendar date of the clinical trial week it was performed to ensure proper recording.

7: At one of the visit, patients will meet with a research psychiatrist to review participation, whether progress or regress is being made, and to complete clinical ratings that will include a Substance Use Inventory, the Clinical Global Impression scale, a medical review, and completion of all clinical notes. All these forms are dated. These are then recorded in the clinical trial week form that corresponds to the calendar dates for that week.

8: At one of the visits, the patients will meet with a STARS or DOSA therapist for compliance enhancement therapy aimed at sustaining compliance with participation in all aspects of the study.

9: If a patient misses a visit, every attempt is made to make contact and reschedule as soon as possible. Significant others reported in the locator form may also be contacted if direct contact with the participant cannot be made. The research team continues this effort until contact is made. If a patient cancels a visit, the patient will be instructed to continue the medication with the "at-home" bottle until the next rescheduled visit.

10: Vouchers for completing all procedures of the study (bringing in the bottle, attending all visits, completing all assessments, attending appointments with the therapist and psychiatrist) will be offered (see Compensation section below).

11: At the end of Phase 2 (week 7), patients are rated as responders or non-responders on the end-of-study (EOS) form. To be a responder, frequency or quantity of cocaine use must have decreased by at least 75% compared to the baseline estimate of the 30 days prior to participation in the study. This is estimated by the results of urine toxicology and self-report recorded on the Time-Line-Follow-Back. If the toxicology does not correspond to the self-report, active use of cocaine is recorded. Missed visit will be recorded as days of use. A secondary measure will be time to relapse of cocaine use after completion of the abstinence induction procedure. They also repeat the salivary cortisol collection, and the stress challenge with intranasal desmopressin.

12: Patients are removed from the trial if they miss one week of medication (3 witnessed administration). Patients may elect to stop their participation at any time. Reasons for cessation will be recorded on the end-of-study form. We will attempt to complete end-of-study assessments. Patients may be removed by the investigator under several circumstances: 1) emergence of a medical condition unrelated to the study that would render continued participation

unsafe; 2) psychiatric worsening, such as emergence of depression (HamD score >17), psychosis (HamD item 22 >3), or of other significant psychiatric symptoms such as suicidality (HamD item 15 > 3), culminating in a CGI score > 6 for two consecutive weeks; 3) substance abuse worsening as assessed by clinicians on the research team during weekly visits, as evidenced by a CGI score >6 for two consecutive weeks; 4) emergence of hyponatremia during the study as indicated by a sodium concentration < 133 mEq/L or early symptoms such as asthenia, fatigue, nausea, vomiting, and weakness; 5) missing one week of supervised clinic-based administration of IN oxytocin or placebo.

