4. Oxytocin: Oxytocin is used during labor and delivery to promote uterine contraction. In this instance, doses vary, but far exceed the daily dose of 24 IU/day used in this study. Administered intravenously as Pitocin, it can also lead to hyponatremia, arrhythmia, convulsions, chest pain, shortness of breath, confusion, swelling, headache, nausea/vomiting, cardiac arrhythmia. During their participation, control participants will receive 2 consecutive doses of IN oxytocin (40 IU in total) during phase 1. Cocaine-dependent patients receive 47 doses of IN oxytocin (940 IU) over a period of 7 weeks. No serious adverse events arose in a study during which 40 IU were administered daily for one week, then 80IU/day for another 7 weeks (Modabbernia et al., 2013). Feeling too relaxed, light-headedness, anxiety, clouded thinking, and nasal cavity irritation are the most common side effects reported in protocols approximating the one presented here (Rodrigues et al., 2009; Ditzen et al., 2009).
  
5. Another potential risk, especially for intranasal cocaine users, is whether the use of the intranasal approach would serve as a trigger for cocaine use. As this pharmacological approach has not been investigated before, this will be specifically queried for during clinic-based administration.
  
6. No data exists examining the risk of cocaine use is enhanced by concomitant intake of oxytocin. We

---

do not anticipate that it would increase the risk of cocaine use. As change in cocaine use is a main outcome of the study, evidence of increased cocaine use will be monitored closely.

7. The stress challenge may cause patients to experience cravings for cocaine. After each procedure, a gradual muscle relaxation procedure will be used to reduce these.
  
8. Vouchers could be exchanged for drugs, or their monetary value could serve as a trigger to procure cocaine. Expending vouchers is a major topic of the counseling during the study to promote a drug-free lifestyle.
  
9. The structured interviews, self-reports, and questionnaires should not pose a physical risk. Their disadvantage is the time to complete them. Our past experience using these measures indicates that patients find them acceptable.
  
10. The risk of the blood tests is the discomfort associated with venipuncture, and a possibility of slight bruising. For the stress challenge, a saline lock will be placed to avoid repeated venipuncture.
  

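### Leftover 20 IU figures contradict the 24 IU/day oxytocin specification in the dosing instruction, stated exposure and bottle-weight target; separately, one removal list uses sodium <130 instead of <133 mEq/L

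*Protocol*

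**What the plan says.** **Main specification.** The Lay Summary and the Design Overview both give 24 IU. Phase 2 item 1 says "Patients continue to receive intranasal Oxytocin (24IU/day) vs. intranasal placebo", and Phase 2 item 2 says "The metered bottle delivers 4 IU/0.1cc or per puff. Each daily dosing requires 6 puffs, or 0.6cc", with an expected weight change of 600 mg per daily dose. On the oxytocin challenge day the patient is asked to "insufflate 12 IU (16 ug or 0.3cc) of oxytocin in each nostril", which is again 24 IU.

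**Text that departs from it.**
- *Protocol, Phase 1 step 5.* Staff are to "begin randomized administration of intranasal Oxytocin 20 IU per day in the morning". The training that follows is one spray in each nostril, and then "repeat steps 1 to 3 again to reach the daily dose of 24 IU of randomized medication".
- *Protocol, Risks item 4.* Labor doses are said to "far exceed the daily dose of 24 IU/day used in this study", yet the exposure statement reads "Cocaine-dependent patients receive 47 doses of IN oxytocin (940 IU) over a period of 7 weeks". For controls it reads "control participants will receive 2 consecutive doses of IN oxytocin (40 IU in total) during phase 1".
- *SAP, Phase 2 Measures, compliance monitoring.* The bottle delivers 5 IU per puff, a daily dose is 4 puffs or 0.4 cc, and the expected weight change is 400 mg.
- *Protocol, Background section 1.4.* The dose proposed in this study is given as 20 IU, in a parenthesis that also holds a literature citation.

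**Sodium.** Phase 2 item 12 and the Criteria for Early Discontinuation list hyponatremia below 133 mEq/L as grounds for removal. The section on minimizing risks interrupts medication below 133, with or without symptoms. Its own removal list, otherwise the same as the other two, says below 130.

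**The concern.** These figures tell staff what to teach, tell readers how much drug is planned, set the yardstick for home adherence and define a safety threshold. Staff who follow the step 5 cycle count literally would teach too few sprays. The SAP's weight target would then score that patient as fully compliant, so the check meant to catch underdosing would miss it. The risk section understates planned exposure for the oxytocin arm and overstates it for controls. It also gives its total for cocaine-dependent patients without distinguishing arms, although placebo patients receive oxytocin only at the challenge.

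The SAP's Primary outcome section already reports results for 26 randomized patients (15 oxytocin, 11 placebo). A reader of those results cannot tell from the documents which daily dose the oxytocin arm was taught.

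**Working it through.** **1. The main specification agrees with itself.**
- Inputs, Phase 2 item 2: 4 IU per 0.1 cc puff, 6 puffs, about 0.1 g per puff.
- Daily dose: 6 x 4 = 24 IU. Weight: 6 x 0.1 g = 600 mg.
- Challenge dose: 0.3 cc / 0.1 cc = 3 puffs per nostril; 3 x 4 = 12 IU; x 2 nostrils = 24 IU.

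**2. Step 5 training.** Two cycles x two nostrils = 4 sprays.

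| Strength used | Dose from 4 sprays | Share of 24 IU |
|---|---|---|
| 4 IU per puff (protocol) | 4 x 4 = 16 IU | 16/24 = 67% |
| 5 IU per puff (SAP) | 4 x 5 = 20 IU | 20/24 = 83% |

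Neither strength gives 24 IU from four sprays. No place in the documents states 16 IU; it combines the step 5 spray count with the Phase 2 bottle strength.

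**3. Stated exposure, Risks item 4.**
- Reproducing the stated total: 940 / 47 = 20 IU per dose. It follows at 20 IU, not at the 24 IU/day named in the same item.
- At 24 IU with the stated count: 47 x 24 = 1,128 IU. The stated figure is 1,128 - 940 = 188 IU too low (188/1,128 = 17%).
- A check that does not depend on the Phase 1 count: Phase 2 is 6 weeks x 7 days = 42 doses; 42 x 24 = 1,008 IU, already 68 IU above 940.
- Controls: 40 / 2 = 20 IU per dose. Oxytocin is given on only one of the two test days (Stress Challenges; SAP Study Assessments), so exposure is 1 x 24 = 24 IU. The stated 40 IU is 16 IU too high. Two doses is right for desmopressin, which is given on both days.
- Placebo patients: the challenge dose only, 24 IU.

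**4. SAP weight target.** The SAP agrees with itself at 20 IU: 4 x 5 = 20 IU and 4 x 0.1 g = 400 mg. It conflicts with the protocol.

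| Puffs taken at home | Against 600 mg (protocol) | Against 400 mg (SAP) |
|---|---|---|
| 6 (600 mg) | 100% | 150% |
| 4 (400 mg) | 67% | 100% |

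Only the protocol target would expose a patient taking four sprays.

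**5. Sodium.** The removal lists differ only for values from 130 to below 133 mEq/L. Each also allows removal on early symptoms alone, so the gap is confined to patients without symptoms. For them, medication is interrupted below 133 in any case.

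**The case against.** **One slip rather than several.** Four sprays of 5 IU make 20 IU, which fits step 5, the risk totals, the SAP and Background section 1.4. This looks like a 20 IU regimen incompletely updated to 24 IU. That is a fair inference, but it does not remove the conflict: the 20 IU figures stand in the current text.

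**A deliberate 20 IU start.** Step 5 itself names 24 IU as the daily dose, the Design Overview starts randomized medication at 24 IU, and Phase 2 item 1 has patients continuing at that dose. A lower starting dose is not supported.

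**Staff would notice.** Step 5 names the 24 IU target, Phase 2 item 2 says 6 puffs, and doses are witnessed three times a week. This makes underdosing a risk rather than a certainty. A reader might go further and infer that patients were underdosed, or that underdosing explains the null result. The documents do not support either: they do not record how many sprays were taught or taken.

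**Background section 1.4 may report the cited study's dose.** The citation makes the parenthesis ambiguous, but the sentence names the dose of this study, so it needs clarifying.

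**Sodium might be two tiers: interrupt below 133, remove below 130.** That fits the risk-minimization section alone, but the two other removal lists use 133. A reader might also infer that patients between 130 and 133 would stay on drug, or that the three-patient stopping rule shifts. Neither follows: interruption applies below 133, and the same section defines hyponatremia at that level.

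**Limited consequence.** Bottle weight enters no planned analysis, and removal is discretionary. This stands and limits the weight of the point.

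**Conclusion.** The contradictions are real and should be fixed. The dosing step yields 67% or 83% of the intended dose, depending on bottle strength. The oxytocin-arm total is 188 IU (17%) too low if 47 doses is right, and at least 68 IU below what Phase 2 alone requires. Control exposure is overstated by 16 IU. The SAP's weight target is two thirds of the protocol's. The sodium difference is separate and small.

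This rests on 24 IU/day being the intended dose, as the main specification says, and on daily dosing through all six weeks of Phase 2. The count of 47 is the protocol's own; the uploaded Phase 1 schedule was not available to check it. The point concerns instructions, stated exposure, the adherence target and one threshold. It does not alter any endpoint, test or power figure.

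**What to change.** 1. **Establish the facts first.** State the bottle strength, the number of sprays taught, the daily dose given and the weight target used for the 26 randomized patients. Rewriting the text to 24 IU before this is known could misdescribe how the trial was run.
2. **If the dose was 24 IU:**
   - Phase 1 step 5: change 20 to 24 IU and teach three spray cycles (6 sprays).
   - Risks item 4: confirm the dose count, then give 47 x 24 = 1,128 IU for the oxytocin arm, the single 24 IU challenge dose for placebo patients, and one 24 IU dose for controls.
   - SAP compliance monitoring: use 4 IU per puff, 6 puffs, 0.6 cc and 600 mg.
   - Background section 1.4: correct the study dose, or separate it from the cited dose.
3. **If it was not 24 IU:** report the dose actually delivered alongside the results.
4. **In either case:** change the removal threshold in the risk-minimization section from 130 to 133 mEq/L.

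The cost is a check of pharmacy and training records plus short wording edits. Design, analysis and sample size are unaffected.

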**The study will be stopped if 3 patients develop hyponatremia during the course of the study.**

**Phase 3 is a repeat of the DDAVP stress challenge and saliva cortisol collection**

Below is a table of measures by week and clinic visits (Table 3).

Table 3: Weekly measures

	Study assessments	Screening	Wk 1 Phase 1	Wk 2 to Wk 7 Phase 2
Physiological measures	Blood studies: chem. 20, CBC. Urinalysis, Urine drug toxicology, urine pregnancy test	XX		
Monitoring blood studies: chem20, CBC.				XX (wk 2,4,6)
EKG		XX		XX (wk 7)
Medical Hx		XX		XX
Physical examination		XX		XX
Urinalysis		XX		XX (wk 2,4,6)
Urine toxicology		XX	XX (daily)	XX (3x/week)
Endocrine Stress Challenge with observed and		XX		XX

subjective ratings			
Supervised IN Oxytocin		XX	XX (3x/week)
BP, Pulse, Temp	XX	XX (daily)	XX (3x/week)
Interviews		XX	XX (3x/week)
TLFB-cocaine	XX	XX	XX (3x/week)
CGI-O	Adverse Symptoms Report (ASR)	XX	XX (1x/week)
Ham-D, 25 items		XX	XX (1x/week)
QSUI		XX	XX (1x/week)
MINI		XX	
Self-Reports		XX	XX (3x/week)
PSS		XX	XX (1x/week)
Cocaine craving scale (CCS)	CGI-self	XX	XX (3x/week)
Locator Form		XX	
Demographic form		XX	
Drug history questionnaire		XX	

